#### 4. Study Procedures

- a. Study design, including the sequence and timing of study procedures (distinguish research procedures from those that are part of routine care).

Research Procedures will be integrated into the routine part of the preoperative pre-anesthesia session. .

A member of the study team will approach the anesthesiologists who will be in the control arm of the study. None of the study team members will be in a supervisory or evaluative role to the potential anesthesiologists to be approached. Patient participants will be approached and asked if they are interested in participating. Those who are interested and eligible will undergo the research informed consent process. Patients will be divided into a **control group** and an **intervention group**. Both groups will receive the above described post-operative questionnaires with the addition of selected questions regarding their prior experience with anesthesia, and their understanding of what the anesthesiologist is responsible for. During the post-operative questionnaire they will also be asked what percentage of the signed anesthesia consent they read and if they recall anything about it. The questionnaire will be completed postoperatively, over the phone or in person, no more than 3 days after the day of the procedure.

The **control group** will have their pre-op discussion performed by an anesthesiologist in a manner commensurate with their routine for preoperative discussion. These anesthesiologists are not part of the study team. These anesthesiologists will be approached by a member of the study team and asked for permission to participate and be observed; then their patients will also be approached for participation. These anesthesiologists will be audio-recorded. Remotely, a study team member will review the audio-recording and will use a check list to assess the content communicated during the preoperative discussion. The amount of time that the discussion takes will also be recorded.

The **intervention group** will have their pre-op discussion performed by one of the two study anesthesiologists who will perform their discussion with knowledge of specific material that must be addressed prior to completion of the discussion including:

1. Description of the type of anesthesia administered
2. Description of what that type of anesthesia is (eg. what is general anesthesia?)

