3. The expected anesthesia related procedures to be performed and the possibility of additional procedures performed if necessary.
4. anesthesia risk
5. Intraoperative communication with the rest of the operating room team
6. Communication to the patient that everything done will be in the interest of safety
7. Plans for pain and nausea control
8. An offer to address any additional questions that the patient may have

These anesthesiologists will also be -audio-recorded. Remotely, a study team member will review the audio-recording and will use a check list to assess the content communicated during the preoperative discussion. The amount of time that the discussion takes will also be recorded.

A comparison of the questionnaire results between the control and intervention groups will be made, and data will be statistically analyzed at the end of the study and data entry period.

- b. If your study involves data/biospecimens from participants enrolled under other research studies with a written consent or under a waiver of consent, please list the IRB application numbers for those studies. Please note: Certificate of Confidentiality (CoC) protections applied to the data in source studies funded by NIH or CDC will extend to this new study if the funding was active in 2016. If this situation applies, Section 36, question 4 in the application will need to be answered “Yes” and “Hopkins Faculty” should be selected in question 7. No other documents are required. N/A
- c. Study duration and number of study visits required of research participants. Study duration is anticipated to be 6 months and does not require any follow up visits from the research participants.
- d. Blinding, including justification for blinding or not blinding the trial, if applicable. Patients will be blinded to the group that they are assigned to. (control vs. intervention).
- e. Justification of why participants will not receive routine care or will have current therapy stopped. This study does not interrupt routine care for patients.
- f. Justification for inclusion of a placebo or non-treatment group.  
A control group is used to show the standard without the intervention and will be used to compare any similarities or differences to outcomes in the intervention group. Having a **control group** eliminates the potential impact of all other variables.
- g. Definition of treatment failure or participant removal criteria.  

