**5. Inclusion/Exclusion Criteria**

Inclusion Criteria: Adult patients undergoing general anesthesia for elective cases

Exclusion Criteria: Patients under age 18; Patients not undergoing general anesthesia

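### Control patients are found through an anesthesiologist already designated as a control, and nothing conceals the arm from whoever recruits, so selection into the two groups can differ

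*Combined protocol and SAP*

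**What the plan says.** Section 4a (Study design) begins with the providers: "A member of the study team will approach the anesthesiologists who will be in the control arm of the study". It then turns to patients: "Those who are interested and eligible will undergo the research informed consent process". Next comes the sentence "Patients will be divided into a control group and an intervention group", with no method of division and no statement of when it happens.

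The control-group paragraph of the same section is more specific. Of the control anesthesiologists it says "These anesthesiologists are not part of the study team", and that they will be "asked for permission to participate and be observed; then their patients will also be approached for participation". The intervention group "will have their pre-op discussion performed by one of the two study anesthesiologists". No order of approach is given for intervention patients.

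Section 4d states: "Patients will be blinded to the group that they are assigned to". It is silent on the person who recruits. Section 4f claims that having a control group removes the influence of every other variable. Eligibility in Section 5 is broad: "Adult patients undergoing general anesthesia for elective cases". Section 7 names recall of risks and understanding of the plan as primary outcomes, and lists Pearson chi-squared and Mann-Whitney tests with no covariate adjustment.

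**The concern.** If the arm is known before a patient is approached, two choices can depend on it: whom the recruiter selects, and how the study is presented. Patients' willingness to agree may follow from the second. Blinding the patient does not address this, because the knowledge sits with the recruiter.

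The primary outcomes plausibly depend on what a patient brings to the discussion, such as health literacy, anxiety and earlier anesthetics. If one arm enrolls more patients who would recall and understand well in any case, the arms will differ even if the structured discussion does nothing. The planned tests would attribute that difference to the discussion. More patients would not help, since a larger sample estimates the same biased difference more precisely.

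**Working it through.** The plan gives no figure on this point, so there is none to reproduce. The check is a reading of the sections against each other.

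1. **When is the arm fixed for a control provider?** Before that provider is approached. Section 4a describes those approached as the ones who will be in the control arm.
2. **How is a control patient found?** Through that provider. Section 4a places the patient approach after the provider's agreement and refers to that provider's own patients. The arm can therefore be known before approach and consent.
3. **Does the provider reveal the arm?** Yes. Intervention discussions come only from the two study anesthesiologists, and control discussions only from anesthesiologists outside the study team. Provider and arm coincide.
4. **And for an intervention patient?** Section 4a gives no sequence. Because provider and arm coincide, the arm is knowable once the case is known to be on a study anesthesiologist's list. This is an inference, not something the text states.
5. **Does anything prevent or reveal arm-aware selection?** Section 4d covers patients only. Section 5 leaves wide latitude over whom to approach. No concealment, consecutive-patient rule or screening log is described. The questionnaire does ask both groups about earlier anesthesia. But it is completed after surgery by enrolled patients, so it cannot show who was passed over or declined, and no between-arm comparison of those items is planned.

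**Illustration of size (all inputs assumed).** Let a share *p* of enrolled patients have high health literacy, with 70% of them recalling the risks against 40% of the others. Expected recall in an arm is *p* × 0.70 + (1 − *p*) × 0.40. With no effect of the discussion, the arms differ by (difference in *p*) × (0.70 − 0.40).

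| Imbalance in *p* | Spurious difference in recall |
|---|---|
| 0 | 0 |
| 0.05 | 0.05 × 0.30 = 1.5 percentage points |
| 0.20 (60% v 40%) | 0.58 − 0.52 = 6 percentage points |
| 0.40 (70% v 30%) | 0.61 − 0.49 = 12 percentage points |

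The sign depends on which arm has the larger share, and nothing in the documents settles that.

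**The case against.** The strongest defense is that the quoted sentence describes only a permission sequence: the provider must agree to be observed and recorded before that provider's patients can sensibly be asked. On that view the order is unavoidable, and the real gap is the absence of concealed allocation. This largely stands. Provider agreement before patient approach is not itself the defect, and the fix below keeps it. What remains is that the plan identifies patients through a provider whose arm is known and does nothing to keep that knowledge from affecting selection.

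Three stronger readings are tempting, and the documents do not support them.

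- **That the protocol contradicts itself by giving two orders, one with allocation after consent.** The sentence about dividing patients carries no timing, and the paragraph containing it also begins with the anesthesiologists. A contradiction would rest on sentence order alone.
- **That the recruiter knows the arm of every patient.** A study team member is named as approaching the anesthesiologists. The approach to patients is in the passive voice with no recruiter named, and no intervention-arm sequence is given.
- **That the problem is independent of who delivers the discussion.** The arm is knowable at approach because provider and arm coincide. If the same people gave both discussions, the quoted sentence would not reveal the arm, and what was left would be the general lack of random, concealed allocation.

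It is also fair to say that the questionnaire items on earlier anesthesia are relevant background data. They mitigate only in part: they do not measure literacy, and they cover enrolled patients only.

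**Conclusion.** The concern holds in limited form. Followed as written, the plan allows the arm of a control patient, and by inference of an intervention patient, to be known to whoever selects, approaches and consents. Nothing in the documents prevents arm-aware recruitment or would reveal it, and the unadjusted tests in Section 7c would not correct for it. The claim in Section 4f that a control group removes the influence of other variables is therefore unsupported.

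The documents show that such bias is possible, not that it will occur. The range of 0 to 12 percentage points rests entirely on an assumed 30-point recall gap and assumed imbalances. Confidence is moderate, because the intervention-arm sequence and the identity of the recruiter are not stated. The change should be made before enrolment.

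**What to change.** State one recruitment procedure for both arms in Section 4a:

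1. Approach every consecutive eligible patient on the lists of the participating control and study anesthesiologists, using the same script.
2. Where feasible, use a recruiter who is not told which anesthesiologist is assigned to the patient. A study team member will probably know who the two study anesthesiologists are, so it is the patient's assignment that must be withheld.
3. Keep a log of eligible, approached and consented patients by arm. Report it with a between-arm comparison of the earlier-anesthesia items already collected.
4. Where the schedule allows either type of anesthesiologist to hold the discussion, assign the arm from a concealed random list opened only after research consent.
5. Delete or qualify the claim in Section 4f.

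Steps 1 to 3 need protocol wording and a screening log, with no extra patients or questionnaire items. They reduce or expose selective recruitment but do not make the two sets of case lists alike; only step 4 addresses that.

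Step 4 costs more. It limits enrolment to days when both types of anesthesiologist are available, and it may change at short notice who holds the discussion. Section 3 notes that first contact usually comes only a few hours before the procedure, and Section 4e says that routine care is not interrupted. The sponsor would need to show that any such change is workable within those limits.

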### 1. Abstract

There is a substantial body of work regarding the written anesthesia consent form. As a result, the written anesthesia consent form has become a standard requirement throughout the United States of America. However, there has been little examination of verbal aspects of anesthesia consent and of the value of the preoperative anesthesia discussion that should take place prior to surgery. Non-anesthesia medical studies have indicated that inadequate patient-physician communication and an inadequate patient-physician relationship will result in misunderstanding and an increased malpractice risk. Lack of understanding of the duties and responsibilities of anesthesiologists is also damaging to the professional status of the field of anesthesiology. This study will utilize patient interviews and questionnaires to examine the degree of awareness that the patients and their families possess regarding what general anesthesia is, the duties and responsibilities of the anesthesiologist, the role of the anesthesiologist within the operating room and the specifics of what they are agreeing to by signing the consent form. If it is determined that a more structured and thorough pre-anesthesia discussion will help patients and their families understand what general anesthesia is, understand the specific responsibilities of anesthesiology providers, understand the professional status of anesthesiologists, give them a better feeling of autonomy and better understand what they are agreeing to by signing the consent form, then there will be substantial ramifications to the priority and importance given to pre-anesthesia discussions nationwide. Secondary benefits include influences on anesthesia residency training and malpractice actions against anesthesiologists. Improved patient satisfaction with the anesthesia experience is another potential secondary benefit.

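### Section 4d blinds patients only; nothing in the available text keeps the person who gives or scores the postoperative questionnaire unaware of the arm

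*Combined protocol and SAP*

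**What the plan says.** Section 4d asks for the blinding arrangements and their justification. The answer covers patients only: "Patients will be blinded to the group that they are assigned to".

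Section 4a sets out how outcomes are collected. "Both groups will receive the above described post-operative questionnaires", with added questions on earlier anesthetics and on what the anesthesiologist is responsible for. "The questionnaire will be completed postoperatively, over the phone or in person", within 3 days of the procedure. Patients are asked about the consent form as well: "they will also be asked what percentage of the signed anesthesia consent they read and if they recall anything about it". The Abstract describes the method in these words: "This study will utilize patient interviews and questionnaires".

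Section 4a also sets out who delivers each arm. Intervention patients have their "pre-op discussion performed by one of the two study anesthesiologists". Of the control anesthesiologists it says: "These anesthesiologists are not part of the study team". They are recruited by the team: "A member of the study team will approach the anesthesiologists who will be in the control arm of the study". In both arms a team member later goes through the audio recording with a checklist.

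Section 7a gives the primary outcome as patients' memory of the risks and their grasp of the anesthetic plan.

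**The concern.** Blinding the patient does not blind the person who asks the questions or judges the answers. Recall and understanding are open to influence at that point. An interviewer who knows the arm may rephrase, wait longer or offer a cue more readily to one group. A grader who knows the arm may give more credit to a vague reply.

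Section 4a bases the between-arm comparison on the questionnaire results, so either habit would feed directly into the primary result. Neither the chi-squared test nor the Mann-Whitney test named in section 7c can detect or correct it. Different prompting cannot be undone once the answers are in, so the safeguard has to be set before data collection.

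**Working it through.** The documents give no sample size, significance level or expected recall rate, and no basis for a size of assessor bias. There is no figure to reproduce and none to derive. The check is therefore a reading of the text in five steps.

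1. **Who is blinded?** Section 4d names patients. No other section names a blinded role.

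2. **Who gives and scores the questionnaire?** Section 4a states the route and the time limit but not the person. It mentions no script, no scoring rule and no separation of duties. Section 7 adds only the outcome names and the tests.

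3. **Would that person be likely to know the arm?** Setting the two delivery statements in section 4a side by side, every intervention discussion is held by one of two named-role study anesthesiologists and every control discussion by someone outside the team. Knowing the provider is enough to know the arm. Three team duties reveal it: delivering the intervention, recruiting control anesthesiologists, and reviewing recordings. Nothing bars people with those duties from giving or scoring the questionnaire.

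4. **Does another provision close the gap?** Three come near.
   - The audio review in section 4a assesses what the anesthesiologist said, not what the patient answered, and the reviewer is not described as masked.
   - De-identification in section 8b removes patient identifiers at data entry. That comes after the questionnaire has been given, and it does not hide the arm from an interviewer.
   - The statement in section 4a that team members do not supervise or evaluate the anesthesiologists approached protects recruitment, not outcome assessment.

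   None of the three masks the assessor.

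5. **By which routes could bias enter?**
   - *Prompting.* A telephone contact implies that someone asks the questions, and the Abstract refers to interviews. This route is open even for fixed-choice items read aloud. It closes only where a patient completes the form alone.
   - *Grading.* This requires items scored by judgement. The one item whose wording suggests this asks what is recalled of the consent form. It could be answered yes or no, and no section says that it counts towards the primary outcome. This route is conditional on the instrument.

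**The case against.** The strongest reply is that the gap is silence about an instrument that cannot be seen. Section 4a refers back to a description of the questionnaires that is not in the available text. It may have been in material removed before publication, and it may have fixed the items, the key and the manner of administration. Patients are said to receive and complete a questionnaire, which is compatible with self-completion when contact is face to face. The tests in section 7c suit fixed-response items, although coded open answers would suit them too. This stands against any firm claim about grading, and the missing description is not counted here as a defect. It does not answer the point about prompting, because the telephone route remains and 4d, where assessor masking belongs, is in the text and stops at patients.

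A second reply is that the remedy depends on staffing that the documents do not describe. That also stands. The cost is low only if someone on the team is free of the arm-revealing duties.

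A third is that the benefit is partial. Patients are divided into groups with no randomisation described, and arm is tied to provider. Differences due to the anesthesiologist or to patient mix would survive perfect assessor masking. This limits what the fix achieves, but assessor bias is a separate source of error with its own remedy.

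**Conclusion.** The point holds in limited form. As written, the plan allows an arm-aware person to collect the primary outcome by telephone or interview, and to grade any open answers. Prompting is the better-supported route; grading is conditional on an instrument that the text does not show.

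A reader might infer more in three ways, and the documents do not support any of them.

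- *That assessors will know the arm, or that the study anesthesiologists will question their own patients.* The plan permits this but does not say it.
- *That the false-positive rate is inflated by some stated amount.* Any such figure would need an assumed sample size, recall rate and degree of favouritism, and none of these has a basis in the text. Prompting would be harder still to quantify. No figure is given for that reason.
- *That masking the assessor would make the arms comparable.* It would not, because arm would still be tied to provider.

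The conclusion rests on the silence of the available text and on a telephone contact involving an interviewer. The change should be made, with medium confidence, because it improves the method at modest cost and leaves the planned analysis as it is.

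**What to change.** Add the following to section 4d.

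- **Interviewer.** The questionnaire is given by an existing team member who is not one of the two study anesthesiologists, did not recruit the anesthesiologist concerned and did not review that patient's recording. This person is not told the arm or the anesthesiologist's name.
- **Script.** A fixed script is used for every contact, by telephone or face to face.
- **Scoring.** Any open answers are written down word for word and scored with the arm hidden, against a key fixed before the first patient. If the instrument already has a key, cite it.
- **Unmasking.** Each occasion on which the interviewer learns the arm is logged.
- **Fallback.** If staffing does not allow a masked interviewer, keep the fixed script and the arm-hidden scoring, and report prompting bias as a remaining limitation. Hidden scoring deals with grading but not with prompting.

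The cost is some reassignment of tasks, a written script, a key if none exists, and less flexible scheduling. Some unmasking is to be expected, because a patient may name the anesthesiologist or repeat the topics covered. No patient visit is added. The report should say that this measure does not deal with confounding by provider.

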Failure of treatment could be failure to complete pre-anesthesia session; participants can be removed if it is later determined that the patient is not eligible; for example, if the patient ended up getting consented for spinal anesthesia instead of general anesthesia.
- h. Description of what happens to participants receiving therapy when study ends or if a participant’s participation in the study ends prematurely. When the study ends, it will not affect a participant’s routine care that is received outside the study. If a participant’s participation

ends prematurely, but after informed consent was obtained, then only the information obtained prior to the end of participation would be used as part of the study. If informed consent is not obtained, participant will not participate in the study. If research consent is obtained but surgery case is cancelled on the day of surgery, participant will be removed from study.

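### A patient whose anesthetic changes can be removed after group assignment, and no analysis set is defined, so the intervention can select the groups being compared

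*Combined protocol and SAP*

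**What the plan says.** Section 4a gives the order of events. Patients consent to the research and then "Patients will be divided into a control group and an intervention group". The pre-operative discussion follows and is itself the intervention. Intervention patients "will have their pre-op discussion performed by one of the two study anesthesiologists", who work from a list of required topics that includes anesthetic type, what it is, expected procedures and risk. Control patients have the usual discussion with anesthesiologists from outside the study team. The only outcome questionnaire is given after surgery, within three days of the procedure.

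Section 4g then says that "participants can be removed if it is later determined that the patient is not eligible". The single illustration it offers is a switch of anesthetic after enrolment, worded as "if the patient ended up getting consented for spinal anesthesia instead of general anesthesia". Section 5 defines eligibility by the anesthetic the patient undergoes and names no time point before the discussion at which this is judged.

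Section 4h adds a second, mandatory removal: "If research consent is obtained but surgery case is cancelled on the day of surgery, participant will be removed from study". When participation ends early, "then only the information obtained prior to the end of participation would be used as part of the study".

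Section 7 names recall of risks and understanding of the plan as the primary outcome, and a chi-squared and a Mann-Whitney test. It states no sample size, alpha, analysis set or rule for analysing patients as assigned.

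**The concern.** A fair comparison needs the analysed groups to be fixed by facts known before the intervention. Here a patient can leave the comparison because of the anesthetic eventually consented to. The tested discussion deals with that subject, and its content and its clinician both differ by group. Some changes of anesthetic will have nothing to do with the discussion, but the rule does not separate these from the rest.

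Two features add to this. Removal is optional, and section 4d describes blinding of patients only, so nothing keeps whoever decides a removal unaware of group. A patient removed before the questionnaire may also supply no primary outcome, and with a three-day window that outcome cannot be recovered later.

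At stake is the difference in recall and understanding. If removals differ by group and the removed patients would have answered worse than the rest, a difference can appear where there is none. If they would have answered better, a real one can be hidden.

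**Working it through.** The plan gives no sample size, power, alpha or removal rate, so it has no figure to reproduce. What follows is an illustration; every numerical input is an assumption.

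**Inputs (assumed).** True recall p = 50% in both groups, so there is no real effect. Share removed: r0 in control, r1 in intervention. Recall that removed patients would have shown: q. Patients assigned per group: n = 100 or 200. Two-sided test at 0.05, critical value 1.96.

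**Formulas.**
- Observed recall after removal: a = (p − r·q)/(1 − r).
- Spurious difference: d = a1 − a0.
- Standard error: SE = √[a0(1 − a0)/(n(1 − r0)) + a1(1 − a1)/(n(1 − r1))].
- False-positive rate: Φ(d/SE − 1.96) + Φ(−d/SE − 1.96).

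**Moderate case:** r0 = 2%, r1 = 10%, q = 30%, n = 100.
- a0 = (0.50 − 0.02 × 0.30)/0.98 = 0.5041
- a1 = (0.50 − 0.10 × 0.30)/0.90 = 0.5222
- d = 1.8 points; SE with 98 and 90 patients = 0.0730; d/SE = 0.249
- False-positive rate = 0.0435 + 0.0136 = 0.057

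**Worst case at 10% removal:** r0 = 0, r1 = 10%, q = 0, n = 100.
- a0 = 0.50; a1 = 0.50/0.90 = 0.5556
- d = 5.6 points; SE with 100 and 90 patients = 0.0724; d/SE = 0.767
- False-positive rate = 0.1165 + 0.0032 = 0.120

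**Range.**

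| Control removed | Intervention removed | Recall of removed | Spurious difference | Error, n = 100 | Error, n = 200 |
|---|---|---|---|---|---|
| 2% | 2% | 30% | 0 | 5.0% | 5.0% |
| 2% | 10% | 50% | 0 | 5.0% | 5.0% |
| 2% | 5% | 30% | 0.6 points | 5.1% | 5.2% |
| 2% | 10% | 30% | 1.8 points | 5.7% | 6.4% |
| 2% | 10% | 10% | 3.6 points | 7.9% | 10.8% |
| 0 | 10% | 0 | 5.6 points | 12.0% | 19.2% |

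The first two rows mark the limit of the concern. Equal removal of similar patients, or removal unrelated to recall, gives no bias. With unequal removal of poor performers the difference grows, and for a given bias the error rate rises with sample size.

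**The case against.** The causal link is inferred. No section says that the choice of anesthetic is made in the discussion. The intervention list asks for a description of the anesthetic, not an offer of alternatives, and section 4g does not say when or why a patient would end up with a spinal. The rule can be read as merely enforcing section 5. This stands as far as it goes: it limits the claim to what can happen. It does not remove the claim, because nothing in the plan confines removal to facts fixed before assignment.

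Keeping patients who received another anesthetic has a price, since one primary objective concerns knowledge of general anesthesia. That also stands, and is why a general-anesthesia-only analysis should still be shown.

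No randomisation is described, and group follows the anesthesiologist. Analysing as assigned does not repair that. Selection after assignment is a further problem, and it can be fixed separately.

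Three stronger readings are tempting and unsupported:
- A reader might infer that an incomplete session is a reason for removal. The text says "Failure of treatment could be failure to complete pre-anesthesia session" and then states the removal rule as a separate item. How patients with incomplete sessions are analysed is simply not stated.
- A reader might infer that such a failure can occur in one group only, because the study anesthesiologists work "with knowledge of specific material that must be addressed prior to completion of the discussion including" a list of topics. A control discussion can also be left unfinished.
- A reader might infer that the rule biases the result at any removal rate. The first two rows of the table show otherwise.

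**Conclusion.** The point holds in this form: the plan permits removal after assignment for an event that the tested discussion, or the clinician giving it, could influence, and it defines no analysis set to guard against this. The compared groups can therefore be selected by the intervention; the documents do not show that they will be.

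The size is unknown, because no removal rate or sample size is given. With 50% true recall, 100 per group and 10% removed from intervention, the false-positive rate is about 6% in the moderate case and about 12% in the worst case, and it stays at 5% when removal is balanced or unrelated to recall. At low removal rates the effect is small. The case for change rests on the structure of the rule and the low cost of correcting it. It is a worthwhile improvement, not a fatal flaw.

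**What to change.** - **Sections 4g and 5:** judge study eligibility by the anesthetic planned at research consent, before the discussion takes place.
- **Section 7c:** define the primary analysis set as every patient who had a pre-operative discussion and then surgery, analysed in the assigned group, including those whose anesthetic changed. Give all of them the questionnaire.
- **Sensitivity analysis:** repeat the comparison in patients who received general anesthesia.
- **Reporting:** give all removals by group and reason. Include same-day cancellations: they too follow assignment and could follow from the discussion, but these patients cannot supply a postoperative questionnaire. Their exclusion is therefore unavoidable for this outcome, and any imbalance should be visible.

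The cost is protocol and analysis wording plus a few more questionnaires. The downside is that a few patients who received another anesthetic stay in the primary set. Clinical care does not change.
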